5.4.2. Secondary efficacy endpoints

Secondary efficacy assessments were based on the full analysis set (FAS) and the per-protocol set (PPS).

Surgical success rates at the subject level are statistically analysed according to categorical indicators and compared between groups.

5.5. Safety analysis

The composite endpoint of target lesion failure at the lesion level from procedure initiation to pre-discharge, along with the incidence rates of individual events, shall be statistically analysed as categorical variables and compared between groups.

Cardiovascular clinical composite endpoints at the subject level from the start of procedure until discharge, along with the incidence rates of various events, were statistically analysed according to classification criteria and compared between groups.

Calculate the number of events, incidence rates, and occurrence counts for all adverse events, related adverse events, and serious adverse events in both groups. Cases of study discontinuation due to adverse events and serious adverse events will be listed in a table. Conduct statistical analysis and intergroup comparisons for the incidence rates of individual adverse events and serious adverse events occurring from postprocedure to discharge.

Device deficiency were described using incidence rates.

The clinical significance of laboratory test results shall be presented in pre- and post-procedure cross-tabulation format, with a list of abnormalities deemed clinically significant.

6. Statistical analysis results

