###### **2) Secondary efficacy endpoints: Procedural success rate (subject level)**

To achieve procedural success (subject level), the following conditions should be met simultaneously:

- a.  $\leq 30\%$  residual stenosis of at least one target lesion immediately after PCI (For ISR and drug balloon-related restenosis, residual stenosis  $< 50\%$  post-procedure)
- b. No major adverse cardiac events (MACE) during post-procedure hospitalization: all-cause death, myocardial infarction (MI) and target lesion revascularisation (TLR).

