### 3) Occurrence of single AE and SAE

Evaluation method: The observation time range is from the start of procedure to pre-discharge. Other possible AEs such as balloon rupture, vessel perforation, dissection, acute occlusion, vasospasm, thrombosis (including in-stent thrombosis), arrhythmia requiring intervention. The incidences of single events are counted, respectively.

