## **(2) Procedure details (0d)**

According to the routine procedure of the hospital, no special operation requirements are added. During this period, the following visit contents need to be completed:

- 1) Vital signs (systolic blood pressure, diastolic blood pressure and heart rate);
- 2) Coronary angiography (patient's lesions, residual stenosis after PCI, etc.);
- 3) Clinical evaluation (study balloon operation, including balloon pushability, passing ability, withdrawal ability, dilation frequency, dilation pressure, etc.; device defects; balloon and stent usage);
- 4) AEs (such as procedure-related complications, including puncture hematoma, vascular dissection, vessel perforation, acute occlusion, etc.);
- 5) Cardiovascular adverse events (including major adverse cardiac events - MACE, target lesion failure - TLF, patient-oriented composite endpoint - PoCE);
- 6) Cardiovascular concomitant medications (anticoagulants, antiplatelets, and statins).

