## **12. Provisions for AE and Device Defect Reporting**

### **12.1 Definition of AE and Provisions for AE Reporting**

Adverse event (AE) refers to an adverse medical event that occurs during the medical device clinical trial, related or unrelated to the investigational medical device.

AEs after treatment with the investigational product must be recorded truthfully in the Adverse Event Form. Record the duration of AEs (that is, from start to end), severity, and correlation with the clinical study as well as the corresponding treatment and other management measures. Follow-up shall be made to the end of the trial or the outcome of adverse events.

In this clinical trial, the following conditions may not be recorded as an AE: 1) hematoma less than 6 cm or a small amount of bleeding at the puncture site; 2) common stress reactions post-procedure, such as fever and weak dorsalis pedis artery pulse; 3) abnormal laboratory indicators post-procedure are clinically significant, but the investigators do not take corresponding treatment measures, and the subjects resolve spontaneously.

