2.2. Safety Evaluation

1) Target lesion failure composite endpoint (TLF) incidence

Any of the following events constituted a TLF:

- a. Cardiovascular death (including cases where the cause of death is uncertain but considered cardiovascular in origin);
- b. Target Vessel-Related Myocardial Infarction (TV-MI);
- c. Clinically-indicated target lesion revascularisation (CI-TLR).

Evaluation method: The observation period spans from the commencement of procedure until discharge. For each subject, the incidence rates of individual events and the composite event rate are calculated.

2) Incidence of the patient-oriented composite endpoint (PoCE)

Any occurrence of the following events constituted a PoCE:

- a. All-cause mortality;
- b. All myocardial infarctions;
- c. All recurrent revascularisation events, including target lesion revascularisation (TLR), target vessel non-target lesion revascularisation (TVR), and non-target vessel revascularisation.

Evaluation method: The observation period spans from the commencement of procedure until discharge. For each subject, the incidence rate of individual events and the composite event rate shall be separately calculated.

3) Incidence of Individual Adverse Events and Serious Adverse Events

Evaluation Method: The observation period spans from the commencement of procedure until discharge. Other potential adverse events include balloon rupture, vascular perforation, dissection, acute occlusion, vasospasm, thrombosis (including in-stent thrombosis), and arrhythmias requiring intervention. The incidence rate of each individual event shall be separately calculated.

4) Incidence of device deficiency

3. Analysis Data Set

Full Analysis Set (FAS): The population defined according to the intention-to-treat principle, comprising all subjects who were randomised and received the study product. For patients with missing primary efficacy endpoint data, worst observation carried forward (WOCF) was applied.

Per-protocol set (PPS): Subgroup of the completed trial population excluding major protocol deviations (e.g., subjects breaching inclusion or exclusion criteria).

Safety Set (SS): Refers to the dataset comprising subjects who used the investigational device and for whom safety endpoints were recorded.

Efficacy analyses will be conducted based on both the full analysis set and the per-protocol set. All baseline demographic analyses utilise data from the full analysis set, while safety evaluations employ the safety set.

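### SAP 5.5 words the comparison of individual AEs and SAEs as post-procedure only, against the endpoint's own window, and no table shell settles which applies

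*SAP*

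**What the plan says.** The endpoint definitions agree with each other. Protocol 5.3.2, item 3, says of single AEs and SAEs: "The observation time range is from the start of procedure to pre-discharge". SAP 2.2, item 3, says the same: "The observation period spans from the commencement of procedure until discharge. Other potential adverse events include balloon rupture, vascular perforation, dissection".

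The analysis text differs. In SAP 5.5 the between-group analysis of individual events is specified as "intergroup comparisons for the incidence rates of individual adverse events and serious adverse events occurring from postprocedure to discharge". In that section the TLF and PoCE comparisons both begin with the procedure.

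Intraprocedural events are collected. Protocol 5.5.2, under the day-0 procedure, lists "AEs (such as procedure-related complications, including puncture hematoma, vascular dissection, vessel perforation, acute occlusion, etc", and the schedules in both documents mark AEs and SAEs for the treatment period as well as for follow-up.

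**The concern.** The study balloon is advanced, inflated and withdrawn on day 0. Balloon rupture can only occur while a balloon is in use. Perforation, dissection, acute occlusion and vasospasm would be expected chiefly then, although that is clinical inference: the Protocol also lists perforation, dissection and acute occlusion among the events to record in follow-up. A comparison that begins after the procedure would omit the period in which the device is most likely to cause harm.

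The wording can also be taken as deliberate. Within SAP 5.5 only the AE/SAE sentence starts after the procedure, so a programmer could reasonably treat the difference as intended. Two programmers could then produce different AE and SAE comparisons from the same SAP.

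**Working it through.** The inconsistency itself involves no calculation, so the texts are set side by side.

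| Place | Events | Start of window | Compared between groups? |
|---|---|---|---|
| Protocol 5.3.2, item 3 | Single AEs/SAEs | Start of procedure | Endpoint definition |
| SAP 2.2, item 3 | Individual AEs/SAEs | Start of procedure | Endpoint definition |
| SAP 5.5, TLF and PoCE | Composites and components | Start of procedure | Yes |
| SAP 5.5, counts and rates | AEs overall, related AEs, SAEs | None stated | Tabulated for both groups |
| SAP 5.5, individual AEs/SAEs | Individual AEs/SAEs | After the procedure | Yes |
| SAP Table 30 | Procedural complications | None stated | Yes, P-value per row |
| SAP Tables 31 to 34 | AEs and SAEs, overall and by SOC/PT | None stated | Yes, P-value column |

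1. **Contradiction.** The fifth row conflicts with the first two, which define the endpoint it is meant to analyse, and departs from the third, which stands in the same section.

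2. **What Table 30 covers.** SAP 2.2 names seven event types. Six have their own row in Table 30: balloon rupture, perforation, dissection, acute occlusion, vasospasm and thrombosis. Arrhythmia requiring intervention has no row and would fall under the table's residual category or appear by preferred term in Tables 32 and 34. Table 30 does not record seriousness or relation to the device.

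3. **What Tables 31 to 34 cover.** Tables 31 and 33 hold the totals, including device-related events and, in Table 31, surgery-related AEs. Tables 32 and 34 break events down by SOC/PT. Read on their own, all four include intraprocedural events.

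4. **What happens if the 5.5 sentence is applied to them.** It is the only text that gives a window for comparing individual AEs and SAEs, and none of the four shells gives another. Followed literally, it removes intraprocedural events from the compared rates, most directly in the by-term Tables 32 and 34. A perforation on day 0 that met the SAE definition would still appear as a complication in Table 30 but would be missing from the compared SAE rate. If the restriction were applied to Tables 32 and 34 but not to 31 and 33, the overall AE and SAE rows would not agree between tables.

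5. **Size.** The documents give no expected AE or SAE rate, so the number of events affected cannot be calculated. As a unit of scale, if the safety set holds the planned 68 subjects per group, each subject whose only event of a given kind was intraprocedural lowers that group's rate by 1/68 = 0.0147, or about 1.5 percentage points.

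**The case against.** The strongest reply is that the SAP as a whole does compare these events. The sentence before the restricted one asks for AE and SAE counts and rates in both groups with no time limit. Table 30 tests rupture, perforation, dissection, acute occlusion and vasospasm directly. Table 33 has an overall SAE row with a P-value. TLF and PoCE run from the start of the procedure. A reader might infer from SAP 5.5 that events during balloon use are left out of the between-group safety comparison altogether; the documents do not support that. This part of the reply stands. What it leaves open is which window governs Tables 31 to 34, because the shells are silent.

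The reply also notes, correctly, that Protocol 6.4.2(5) makes the safety analysis descriptive and that the pass/fail rule in Protocol 6.4.5 rests on device success alone.

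Two further inferences are tempting and should not be drawn.

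- Protocol 12.1 says "AEs after treatment with the investigational product must be recorded truthfully in the Adverse Event Form". Taken alone, this could suggest that control-arm or intraprocedural AEs go unrecorded. But the same section first defines an AE as any such event during the trial whether or not related to the device, day-0 collection applies to every subject, and the tables report both groups.
- Procedural success requires "No major adverse cardiac events (MACE) during post-procedure hospitalization". This is not a similar contradiction. That window is used consistently in the Protocol abstract, Protocol 5.3.1, SAP 2.1.2 and the note to SAP Table 23. Moving it would redefine a secondary endpoint, which is a different matter from aligning an analysis sentence with its endpoint.

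The missing arrhythmia row is likewise a matter of presentation, since those events have other places to appear.

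**Conclusion.** The inconsistency is real: SAP 5.5 restricts the comparison of individual AEs and SAEs to the post-procedure period, while the SAP's own endpoint definition and the Protocol's start at the procedure. The consequence is an ambiguity in Tables 31 to 34, not a planned exclusion of intraprocedural events from every comparison.

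The weight is minor to moderate. No margin, hypothesis or pass/fail rule depends on safety, and the events are collected either way. The practical risk rests on one assumption, that whoever programs the tables takes the 5.5 sentence as the governing window. If they follow SAP 2.2 instead, nothing is lost. Because the trial is open-label, the choice should be settled in writing before the results are known.

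**What to change.** In SAP 5.5, change the window in the sentence on individual AEs and SAEs to run *from the start of the procedure to discharge*. State the same window in the notes to Tables 30 to 34.

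This is a change of wording only. It needs no new data, since AEs and SAEs are already collected on day 0, and no change to the sample size or the primary analysis. It should be made before database lock, the point by which Protocol 6.4.7 requires the SAP to be final. The downside is that reported AE and SAE rates will be slightly higher than under a post-procedure window.

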6.1. Subject distribution

Table 1 Case distribution across centres

Centre Code	Research Centre	Group	Number					Exclusion rate (%)	Completed
			Screening Failure	Screening Enrolment	Dropout Count	Dropout rate (%)	Dropout of exclusions		
01	Centre 1	Experimental Group							
		Control Group							
		Total							
02	Centre 2	Experimental group							
		Control group							
		Total							
03	Centre 3	Experimental group							
		Control group							
		Total							
.....									
	Total	Experimental group							
		Control group							
		Total							

Note 1: Number of completions = Number enrolled - Number of dropouts.

Note 2: Exclusion refers to subjects who completed the trial but were not included in the PPS set.

Table 2 Subject Grouping by Centre

Centre Name	FAS		Total	PPS		Total	SS		Total
	Experimental Group	Control Group		Experimental group	Control Group		Experimental group	Control group	
01									

Centre Name	FAS			PPS			SS		
	Experimental Group	Control Group	Total	Experimental group	Control Group	Total	Experimental group	Control group	Total
02									
03									
.....									
Total									

Table 3 Enrolled Cases and Safety/Efficacy Analysis Dataset

Item	Indicator	Experimental Group	Control Group	Total
Screening	Screening conducted			
	Screening Failure			
Randomisation status	Randomised allocation			
Trial completion status	Trial not completed			
	Completed trial			
Reasons for trial discontinuation	Subject declined to continue participation in the study for any reason			
	Withdrawal deemed necessary by the investigator for medical or safety reasons			
	Serious protocol deviation (as confirmed by the principal investigator)			
	Serious protocol deviation by the subject or alteration of the treatment regimen during the trial			
	Death			
	Other			
	Total			

6.2. Demographics and Baseline Parameters (FAS)

6.2.1. Demographic information

Table 4 Population Demographic Information

Item	Indicator	Experimental Group	Control Group	Total
Gender	Male n(%)			
	Female n(%)			
	Total (Missing)			
	Statistic			

Item	Indicator	Experimental Group	Control Group	Total
Age (years)	P-value			
	N(Missing)			
	Mean (SD)			
	Median			
	Q1, Q3			
	Min, Max			
	Statistic			
	P-value			
Weight (kg)	N (Missing)			
	Mean (SD)			
	Median			
	Q1, Q3			
	Min, Max			
	Statistic			
	P-value			
Height (cm)	N (Missing)			
	Mean (SD)			
	Median			
	Q1, Q3			
	Min, Max			
	Statistic			
	P-value			
BMI (kg/m ²)	N (Missing)			
	Mean (SD)			
	Median			
	Q1, Q3			
	Min, Max			
	Statistic			
	P-value			

Note: Age = (Date of informed consent signature - Date of birth) / 365.4375, rounded down.

6.2.2. Medical History

Table 5 Medical History

Item	Indicator	Experimental Group	Control Group	Total
Angina pectoris	None n(%)			
	Yes n(%)			
	Total (Missing)			
	Statistic			
	P-value			
Type of angina pectoris	Stable n(%)			
	Unstable n(%)			
	Total (Missing)			
	Statistic			
	P-value			
Myocardial infarction	None n(%)			
	Yes n(%)			
	Total (Missing)			
	Statistic			
	P-value			
Type of myocardial infarction	Old myocardial infarction n(%)			
	Acute myocardial infarction n(%)			
	Total (Missing)			
	Statistical measure			
	P-value			
Heart failure	None n(%)			
	Yes n(%)			
	Total (Missing)			
	Statistic			
	P-value			
NYHA classification	Class I n(%)			
	Class II n(%)			
	Grade III n(%)			
	Class IV n(%)			
	Total (Missing)			
	Statistic			
Left ventricular ejection fraction (LVEF)	N (Missing)			
	Mean (SD)			
	Median			

Item	Indicator	Experimental Group	Control Group	Total
Stroke	Q1, Q3			
	Min, Max			
	Statistic			
	P-value			
	None n(%)			
	Yes n(%)			
	Total (Missing)			
	Statistic			
Stroke type	P-value			
	Ischemic n(%)			
	Haemorrhagic n(%)			
	Mixed n(%)			
	Total (Missing)			
	Statistical Measure			
	P-value			
Type of haemorrhage in stroke	Intracerebral haemorrhage n(%)			
	Subarachnoid haemorrhage n(%)			
	Ventricle haemorrhage n(%)			
	Other n(%)			
	Total (Missing)			
	Statistical measure			
	P-value			
History of active peptic ulcer	None n(%)			
	Yes n(%)			
	Total (Missing)			
	Statistic			
	P-value			
History of allergies	None n(%)			
	Yes n(%)			
	Total (Missing)			
	Statistic			
	P-value			
Other diseases	None n(%)			
	Yes n(%)			
	Total (Missing)			
	Statistic			

Item	Indicator	Experimental Group	Control Group	Total
P-value				

6.2.3. Screening Period Examination

Table 6 Screening Period Vital Signs

Item	Indicator	Experimental group	Control Group	Total
Systolic Pressure (mmHg)	Blood N (Missing)			
	Mean (SD)			
	Median			
	Q1, Q3			
	Min, Max			
	Statistic			
	P value			
Diastolic pressure (mmHg)	blood N(Missing)			
	Mean (SD)			
	Median			
	Q1, Q3			
	Min, Max			
	Statistic			
	P-value			
Heart rate (beats per minute)	N(Missing)			
	Mean (SD)			
	Median			
	Q1, Q3			
	Min, Max			
	Statistic			
	P-value			

Table 7 Screening Period Coagulation Function

Item	Indicator	Experimental group	Control Group	Total
Prothrombin (PT)	Time Normal Range n(%)			
	Abnormal without clinical significance n(%)			
	Clinically significant abnormality n(%)			
	Not tested n(%)			
	Total (Missing)			
	Statistic			
	P-value			
Activated partial thromboplastin time	Normal range n(%)			
	Abnormal without clinical significance n(%)			

Item	Indicator	Experimental group	Control Group	Total
(APTT)	Clinically significant abnormality n(%)			
	Not determined n(%)			
	Total (Missing)			
	Statistical measure			
	P-value			
Fibrinogen level	Normal range n(%)			
(FIB)	Abnormal without clinical significance n(%)			
	Clinically Significant Abnormal n(%)			
	Not determined n(%)			
	Total (Missing)			
	Statistical measure			
	P-value			
Thrombin time (TT)	Normal range n(%)			
	Abnormal without clinical significance n(%)			
	Clinically significant abnormality n(%)			
	Not tested n(%)			
	Total (Missing)			
	Statistical measure			
	P-value			

Table 8 Screening period pregnancy test

Item	Indicator	Experimental group	Control Group	Total
Pregnancy screening conducted	No n(%)			
	Yes n(%)			
	Total (Missing)			
	Statistical measure			
	P-value			
Reason for non-performance	Following bilateral salpingectomy n(%)			
	Post-hysterectomy n(%)			
	Postmenopausal n(%)			
	Other n(%)			
	Total (Missing)			
	Statistic			
	P-value			
Pregnancy Screening Item	Urinary pregnancy test n(%)			
	Blood pregnancy test n(%)			
	Total (Missing)			
	Statistical measure			

Item	Indicator	Experimental group	Control Group	Total
Pregnancy Qualitative Result	P-value			
	Negative n(%)			
	Positive n(%)			
	Total (Missing)			
	Statistic			
	P-value			

6.3. Protocol Deviation (SS)

Table 9 Protocol Deviation

Item	Indicator	Experimental Group	Control Group	Total
Protocol Deviation	No n(%)			
	Yes n(%)			
	Total (Missing)			
	Statistic			
	P-value			

6.4. Combination therapy (SS)

Table 10 Combined Medication (Anticoagulants, Antiplatelet Agents and Statins)

Item	Indicator	Experimental group	Control Group	Total
Combination Therapy	None n(%)			
	Yes n(%)			
	Total (Missing)			
	Statistical measure			
	P-value			

6.5. Procedure records (FAS)

Table 11 Number of target lesions

Item	Indicator	Experimental group	Control Group	Total
Number of Target Lesions	1 n(%)			
	2 lesions n(%)			
			
	Total (Missing)			
	Statistic			
	P-value			

Note: The number of target lesions is based on the target lesion sites recorded during the use of the test balloon in the procedure. The same applies below.

Table 12 Preprocedure target lesion coronary angiography (by lesion level)

Item	Indicator	Experimental Group	Control Group	Total
Target lesion length (mm)	N(Missing)			
	Mean (SD)			
	Median			
	Q1, Q3			
	Min, Max			
	Statistic			
	P-value			
Reference Vessel Diameter (mm)	N(Missing)			
	Mean (SD)			
	Median			
	Q1, Q3			
	Min, Max			
	Statistic			
	P-value			
Preprocedure target lesion stenosis (%)	N (Missing)			
	Mean (SD)			
	Median			
	Q1, Q3			
	Min, Max			
	Statistic			
	P-value			
Coronary artery lesion type*				
	n(%)			
	n(%)			
	n(%)			
	n(%)			
	Total (Missing)			
	Statistic			
	P-value			
Restenotic Lesion	In-stent restenosis n(%)			
	Drug-eluting balloon restenosis lesions n(%)			
	Other n(%)			
	Total (Missing)			
	Statistical measure			
	P-value			

Item	Indicator	Experimental Group	Control Group	Total
Calcified lesions	None/Mild n(%)			
	Moderate n(%)			
	Severe n(%)			
	None n(%)			
	Total (Missing)			
	Statistic			
	P-value			
Distorted lesions	Yes n(%)			
	No n(%)			
	Total (Missing)			
	Statistic			
	P-value			

*Note: Analysis of lesion types based on core laboratory data: XXX.

Table 13 Non-trial balloon pre-dilatation

Item	Indicator	Experimental group	Control Group	Total
Use of non-trial balloon pre-dilatation*	Yes n(%)			
	No n(%)			
	Total (Missing)			
	Statistical measure			
	P-value			
Number of pre-expansion balloons*	1 n(%)			
	2 n(%)			
	3 n(%)			
	4 n(%)			
	5 n(%)			
	Total (Missing)			
	Statistic			
	P-value			
Diameter (mm)	N(Missing)			
	Mean (SD)			
	Median			
	Q1, Q3			
	Min, Max			
	Statistic			
	P-value			

Item	Indicator	Experimental group	Control Group	Total
Length (mm)	N(Missing)			
	Mean (SD)			
	Median			
	Q1, Q3			
	Min, Max			
	Statistic			
	P-value			
Maximum expansion pressure (atm)	N(Missing)			
	Mean (SD)			
	Median			
	Q1, Q3			
	Min,Max			
	Statistic			
	P-value			
Expansion time (s)	N(Missing)			
	Mean (SD)			
	Median			
	Q1, Q3			
	Min, Max			
	Statistic			
	P-value			

Note: Analyses by device level, except for *use of non-trial balloon pre-dilatation and *number of pre-dilatation balloons at lesion level.

Table 14 Use of Study Balloons

Item	Indicator	Experimental group	Control Group	Total
Number of Balloons*	1 n(%)			
	2 n(%)			
n(%)			
	Total (Missing)			
	Statistic			
	P-value			
Balloon size in experimental group	2.00*10 n (%)			
	2.00*15 n(%)			
n(%)			
	Total (Missing)			
	Statistic			

Item	Indicator	Experimental group	Control Group	Total
Control group balloon size	P-value			
	2.00*13 n (%)			
	2.25*13 n(%)			
n(%)			
	Total (Missing)			
	Statistical			
	measure			
	P-value			
	N(Missing)			
	Mean (SD)			
Diameter (mm)	Median			
	Q1, Q3			
	Min, Max			
	Statistic			
	P-value			
	N(Missing)			
	Mean (SD)			
	Median			
	Q1, Q3			
	Min, Max			
Length (mm)	Statistic			
	P-value			
	N(Missing)			
	Mean (SD)			
	Median			
	Q1, Q3			
	Min, Max			
	Statistic			
	P-value			
	N(Missing)			
Maximum expansion pressure (atm)	Mean (SD)			
	Median			
	Q1, Q3			
	Min,Max			
	Statistic			
	P-value			
	N(Missing)			
	Mean (SD)			
	Median			
	Q1, Q3			
Expansion time (s)	Min, Max			
	Statistic			
	P-value			
	N(Missing)			
	Mean (SD)			
	Median			
	Q1, Q3			
	Min, Max			
	Statistic			
	P-value			

Note: Except for the analysis of the number of balloons at the lesion level, all others are device-level analyses.

Table 15 Stent implantation status

Item	Indicator	Experimental group	Control Group	Total
Stent Implantation*	Yes n(%)			
	No n(%)			
	Total (Missing)			
	Statistic			
	P-value			
Number of stents implanted*	1 n(%)			
	2 n(%)			
	3 n(%)			
	4 n(%)			
	5 n(%)			
	Total (Missing)			
	Statistic			
	P-value			
Stent diameter (mm)	N(Missing)			
	Mean (SD)			
	Median			
	Q1, Q3			
	Min, Max			
	Statistic			
	P-value			
Stent Length (mm)	N(Missing)			
	Mean (SD)			
	Median			
	Q1, Q3			
	Min, Max			
	Statistic			
	P-value			
Maximum expansion pressure (atm)	N(Missing)			
	Mean (SD)			
	Median			
	Q1, Q3			
	Min,Max			
	Statistic			
	P-value			
	N(Missing)			
	Mean (SD)			
	Median			
Maximum expansion time (s)	N(Missing)			
	Mean (SD)			
	Median			

Item	Indicator	Experimental group	Control Group	Total
	Q1, Q3			
	Min,Max			
	Statistic			
	P-value			

Note: Analyses at the lesion level are indicated by * for stent implantation status and * for number of stents implanted; all others are device-level analyses.

Table 16 Drug-coated balloon usage status

Item	Indicator	Experimental group	Control Group	Total
Use of drug-coated balloon*	Yes n(%)			
	No n(%)			
	Total (Missing)			
	Statistical measure			
	P-value			
Number of drug-coated balloons*	1 n(%)			
	2 n(%)			
	3 n(%)			
	4 n(%)			
	5 n(%)			
	Total (Missing)			
	Statistic			
	P-value			
Diameter (mm)	N(Missing)			
	Mean (SD)			
	Median			
	Q1, Q3			
	Min, Max			
	Statistic			
	P-value			
Length (mm)	N(Missing)			
	Mean (SD)			
	Median			
	Q1, Q3			
	Min, Max			
	Statistic			
	P-value			
Maximum expansion pressure (atm)	N(Missing)			
	Mean (SD)			
	Median			

Item	Indicator	Experimental group	Control Group	Total
Maximum expansion time (s)	Q1, Q3			
	Min,Max			
	Statistic			
	P-value			
	N(Missing)			
	Mean (SD)			
	Median			
	Q1, Q3			
	Min,Max			
	Statistic			
	P-value			

Note: Analyses at the lesion level exclude *use of drug-coated balloons and *number of drug-coated balloons; all others are at the device level.

Table 17 Balloon Post-dilation

Item	Indicator	Experimental group	Control group	Total
Use of post-balloon dilatation*	Yes n(%)			
	No n(%)			
	Total (Missing)			
	Statistical measure			
	P-value			
Number of balloons*	1 n(%)			
	2 n(%)			
	3 n(%)			
	4 n(%)			
	5 n(%)			
	Total (Missing)			
	Statistic			
Balloon type	P-value			
	Cutting balloon n(%)			
	Scoring balloon n(%)			
	Mammary balloon n(%)			
	Rotational atherectomy n(%)			
	Laser ablation n(%)			
	Other n(%)			
	Total (Missing)			
	Statistical measure			
	P-value			

Item	Indicator	Experimental group	Control group	Total
Diameter (mm)	N(Missing)			
	Mean (SD)			
	Median			
	Q1, Q3			
	Min, Max			
	Statistic			
	P-value			
Length (mm)	N(Missing)			
	Mean (SD)			
	Median			
	Q1, Q3			
	Min, Max			
	Statistic			
	P-value			
Maximum expansion pressure (atm)	N(Missing)			
	Mean (SD)			
	Median			
	Q1, Q3			
	Min,Max			
	Statistic			
	P-value			
Expansion time (s)	N(Missing)			
	Mean (SD)			
	Median			
	Q1, Q3			
	Min, Max			
	Statistic			
	P-value			

Note: Analyses at the lesion level exclude *use of drug-coated balloons and *number of drug-coated balloons; all others are at the device level.

